## **I. Research Background and Scientific Basis**

Over the past few decades, the prevalence of hypertension among Chinese citizens has risen significantly, with approximately 27.9% of adults currently affected by the condition. Timely intervention targeting factors that elevate blood pressure is crucial for delaying the progression of hypertension and preventing cardiovascular and cerebrovascular diseases. Some patients with early blood pressure abnormalities (130-139/80-89 mmHg) may prioritize lifestyle interventions. Following effective non-pharmacological treatment, some patients achieve normal blood pressure (below 120/80 mmHg), while others fail to normalize or even experience further increases. Persistent elevated blood pressure may indicate that contributing factors remain unaddressed, potentially rendering non-pharmacological approaches ineffective.

### **(1) The Therapeutic Effects of CPAP on Blood Pressure Abnormalities**

Obstructive sleep apnea (OSA) is a highly prevalent respiratory disorder. Current estimates indicate that approximately 176 million people in China suffer from OSA, with 67 million classified as having moderate to severe OSA. Numerous studies indicate that OSA is a significant risk factor for hypertension. Patients with OSA experience recurrent upper airway obstruction during the night, which not only leads to intermittent hypoxemia but also causes autonomic nervous system dysfunction. Excessive sympathetic nervous system activation at night results in significant fluctuations in blood pressure within a short period, even accompanied by a blunted baroreflex response. Simultaneously, OSA causes fragmented sleep and sleep deprivation at night, leading to poor daytime alertness and mood in patients. This results in elevated sympathetic activity throughout the day, causing a significant increase in daytime blood pressure.

Continuous positive airway pressure (CPAP) is the primary treatment for moderate-to-severe obstructive sleep apnea (OSA). It maintains upper airway patency through an “airway support” mechanism, thereby eliminating respiratory events. Although numerous studies indicate that OSA patients experience blood pressure benefits following CPAP therapy, However, results from

numerous studies collectively indicate that the degree of blood pressure improvement following CPAP therapy is not entirely satisfactory. For example, in a meta-analysis involving 1,904 patients, Following CPAP therapy, daytime systolic and diastolic blood pressure decreased by 3.55 mmHg and 2.97 mmHg, respectively; nighttime systolic and diastolic blood pressure decreased by 3.67 mmHg and 2.33 mmHg, respectively. Although the downward trend in blood pressure was statistically significant, the magnitude of improvement was disappointing. Even in a study published by Ou in 2024, blood pressure did not show significant improvement after 6 months of CPAP treatment. Evidently, some hypertensive patients with combined OSA do not experience blood pressure benefits following effective CPAP therapy. Investigating factors influencing CPAP treatment outcomes is crucial for selecting suitable hypertensive patients for CPAP therapy and tailoring individualized intervention approaches.

## **(2) Patients with OSA-related blood pressure fluctuations may be candidates for blood pressure benefits from CPAP therapy**

Patients with OSA often exhibit non-dipping blood pressure and elevated morning blood pressure. Studies indicate that patients with OSA-induced blood pressure rhythm abnormalities are more likely to benefit from CPAP therapy. For example, studies by Pengo et al. confirm that OSA patients with non-spoon-shaped blood pressure profiles experience significant blood pressure reduction following CPAP therapy, whereas those with spoon-shaped blood pressure profiles show minimal improvement in blood pressure after CPAP treatment. Domestic scholars have found that patients with significantly elevated pulse transit time (PTT)-blood pressure due to OSA experience marked improvement in office blood pressure following CPAP therapy. However, while PPT-BP can reflect trends in blood pressure changes, its readings exhibit significant fluctuations and may differ from actual blood pressure levels. This discrepancy is particularly noticeable in the measurement of blood pressure troughs and peaks, where errors frequently occur; Conventional ambulatory blood pressure monitoring can only measure blood pressure intermittently, clearly failing to capture the transient effects of respiratory events on blood pressure. Considering that

blood pressure may fluctuate dramatically within a short timeframe during sleep-related respiratory events, Developing reliable technology capable of continuously recording noninvasive blood pressure holds significant value for identifying patients with OSA-related hypertension and screening individuals who may benefit from CPAP therapy.

Our research group will employ novel volumetric clamping technology to precisely measure beat-by-beat blood pressure, Furthermore, by precisely integrating it with sleep parameters, we developed a sleep-blood pressure index that accurately reflects blood pressure fluctuations during respiratory events and explored its predictive value for CPAP treatment outcomes.

### **(3) Sleep aids may improve sleep quality and enhance CPAP compliance, potentially increasing blood pressure benefits**

Numerous studies indicate that CPAP usage duration is one of the most critical factors determining cardiovascular benefits in patients with obstructive sleep apnea. However, many OSA patients also suffer from severe insomnia, making it difficult for them to tolerate CPAP therapy. At the same time, some OSA patients experience a lowered arousal threshold after CPAP treatment, Difficulty falling asleep and early morning awakenings significantly impair CPAP treatment adherence.

Therefore, insomnia and awakenings may be factors affecting CPAP treatment compliance, thereby reducing blood pressure benefits in OSA patients. Recent studies indicate that trazodone reduces post-CPAP awakenings and improves CPAP treatment adherence, Therefore, we hypothesize that administering sleep aids to OSA patients experiencing insomnia and wakefulness may improve sleep quality following CPAP therapy, enhance CPAP compliance, and potentially increase blood pressure benefits.

This study will conduct a cohort analysis involving patients with early-stage blood pressure abnormalities who have not received drug therapy, as well as hypertensive patients requesting non-pharmacological blood pressure management.

The objectives are: ① to identify OSA patients likely to benefit from blood pressure control using

an innovative sleep-blood pressure index; ② to examine the impact of insomnia and arousal following CPAP therapy on blood pressure; ③ to enhance sleep quality with sleep aids, thereby improving CPAP treatment adherence and blood pressure outcomes. This study will provide novel insights and solutions to address the challenge of uncontrolled blood pressure following CPAP therapy for OSA.

## **II. Research Objectives and Content**

### **1. Research Objectives**

1.1 Validate innovative sleep-blood pressure parameters for screening OSA patients who benefit from blood pressure improvement after CPAP therapy.

1.2 Identify reasons for suboptimal blood pressure improvement in OSA patients after CPAP therapy through analysis of treated patients.

1.3 Improve CPAP treatment compliance and enhance blood pressure benefits by administering trazodone or zopiclone for insomnia and post-CPAP arousals (including micro-arousals).

### **2. Research Content**

2.1 Screen OSA patients likely to benefit using an innovative sleep-blood pressure index: Develop the sleep-blood pressure index by precisely measuring continuous blood pressure via novel volumetric clamping technology and synchronizing it with PSG through engineering techniques. Conduct a cohort study to analyze characteristics of patients with blood pressure improvement after CPAP therapy, obtaining a sleep-blood pressure index and its cutoff value for predicting CPAP treatment benefits.

2.2 Exploring Factors Influencing Blood Pressure Improvement After CPAP Therapy: Compare differences in sleep-related parameters—including insomnia indices, arousal-related indices, and autonomic function—between patients with and without blood pressure improvement after 3 months of CPAP therapy. Analyze residual sleep factors affecting CPAP efficacy.

2.3 Enhancing CPAP Compliance and Blood Pressure Benefits in OSA Patients: Select patients with pre-CPAP insomnia or frequent post-CPAP arousals. Administer trazodone or zopiclone for 4 weeks alongside CPAP therapy. Demonstrate how sleep aids improve sleep quality in OSA patients, thereby increasing CPAP compliance and enhancing blood pressure outcomes.

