#### **4. Key Scientific Questions:**

Scientific Question 1: How can we predict which individuals are likely to benefit from CPAP therapy before treatment initiation?

Solution: Administer an innovative sleep-blood pressure index to patients with moderate-to-severe OSA and initiate CPAP therapy, demonstrating that the sleep-blood pressure index can predict blood pressure improvement following CPAP treatment.

Scientific Question 2: Why is blood pressure improvement limited in OSA patients after CPAP therapy?

Solution: Investigate the relationship between sleep parameters and clinical improvements post-CPAP therapy, identifying insomnia and arousal as key factors limiting treatment benefits in OSA patients.

Scientific Question 3: How can we enhance blood pressure benefits in OSA patients following CPAP therapy?

Solution: Improve CPAP adherence by administering sleep aids to specific patient groups, thereby increasing blood pressure benefits in OSA patients.

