4. Pharmacological Intervention: For patients with OSA and insomnia selected in Study Component 3, or those experiencing frequent awakenings despite CPAP therapy, combined CPAP and trazodone (or zopiclone) treatment was recommended. The treatment regimen involves taking trazodone at an initial dose of 25-50 mg/night before bedtime. Based on patient tolerance and efficacy, the dose may be increased by 25 mg every 3-5 days, not exceeding a maximum of 150 mg/night. Zopiclone should start at 3.75-7.5 mg/night, adjustable to 7.5 mg/night as appropriate. The total treatment period was 4 weeks. Changes in subjective and objective sleep quality before and after medication were recorded using questionnaires, actigraphs, and polysomnography. During follow-up, patients were naturally grouped based on treatment choice and adherence: CPAP alone, CPAP plus trazodone, trazodone alone, and untreated. Compare baseline-to-endpoint blood pressure changes across groups, including intra-group comparisons and inter-group comparisons of rate of change.

5. Sample Size Estimation: Based on the research team's preliminary findings, this project will enroll 120 OSA patients receiving CPAP therapy (Research Content 1-2) and 80 patients with insomnia combined with OSA or frequent awakenings during CPAP use (Research Content 3).

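### Contents 1-2 treat every patient with CPAP and describe no comparator, so they can show what predicts blood pressure change during CPAP, not who benefits from CPAP

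*Protocol*

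**What the plan says.** **Who is treated.** Protocol III.5 states that "this project will enroll 120 OSA patients receiving CPAP therapy (Research Content 1-2"). The inclusion criteria require each participant to agree to three months of CPAP. Objective 1.2 in II.1 reads "Identify reasons for suboptimal blood pressure improvement in OSA patients after CPAP therapy through analysis of treated patients".

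**What is compared.** II.2 (2.2) compares sleep-related parameters "between patients with and without blood pressure improvement after 3 months of CPAP therapy".

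**What is concluded.**
- II.2 (2.1) characterises "patients with blood pressure improvement after CPAP therapy, obtaining a sleep-blood pressure index and its cutoff value for predicting CPAP treatment benefits".
- II.2 (2.2) ends with "Analyze residual sleep factors affecting CPAP efficacy".
- II.1 (1.1) seeks parameters "for screening OSA patients who benefit from blood pressure improvement after CPAP therapy".
- II.4, Question 1 asks "How can we predict which individuals are likely to benefit from CPAP therapy before treatment initiation". The solution to Question 2 names insomnia and arousal as limits on treatment benefit.
- IV.(1), item 1 expects the index to single out patients who will probably benefit from CPAP.

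One passage is narrower. The solution to Question 1 in II.4 speaks only of "demonstrating that the sleep-blood pressure index can predict blood pressure improvement following CPAP treatment".

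The only groups without CPAP (trazodone alone, and untreated) appear in III.4. That section concerns Study Component 3, and its groups form by the patients' treatment choice and adherence.

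**The concern.** Benefit from CPAP is the difference between a patient's blood pressure on CPAP and what it would have been without CPAP. When everyone is treated, the second quantity is observed for nobody and estimated for no group. The label *improved* then combines any CPAP effect with ordinary variation and with change from any other cause. An index that predicts change for any of these reasons gives the same result as one that predicts CPAP benefit.

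The error also runs the other way. Patients with identical CPAP effects will fall on both sides of the split, and 2.2 would then look for what limited efficacy in those labelled *not improved*.

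At stake is how the result is used. A cutoff reported as selecting patients who benefit could guide who is offered CPAP, and insomnia and arousal could be reported as limiting CPAP efficacy, when the design tests neither claim.

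**Working it through.** **Step 1: is there a comparator for the 120?** III.5 assigns 120 patients on CPAP to Contents 1-2 and 80 patients to Content 3. No untreated, sham or delayed-CPAP group is described for the 120. The non-CPAP groups in III.4 belong to Component 3 and are self-selected, and nothing assigns them to Contents 1-2. The protocol gives no inputs from which the 120 could be recomputed, and this point does not depend on that figure.

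**Step 2: can a later analysis plan supply what is missing?** No. Separating a predictor of benefit from a predictor of change needs data on comparable patients without CPAP, and none are planned for Contents 1-2.

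**Step 3: how large could the mislabelling be?** This is an illustration.

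Inputs:
- From the protocol, I.(1): mean fall in daytime systolic pressure after CPAP, 3.55 mmHg (a cited meta-analysis).
- Assumed: *improved* means a fall of at least 5 mmHg; normally distributed change; office-type readings with SD 12-15 mmHg and retest correlation r of 0.6-0.8; ambulatory-type readings with SD 10-12 mmHg and r of 0.8-0.9; baseline separate from the entry reading.

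Formulas:
- SD of change = SD × √(2(1 − r))
- P(improved) = 1 − Φ((5 − effect) / SD of change)

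SD of change at the ends of the ranges:
- Office-type: 12 × √0.4 = 7.59; 15 × √0.8 = 13.42
- Ambulatory-type: 10 × √0.2 = 4.47; 12 × √0.4 = 7.59

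| SD of change (mmHg) | Improved, effect 0 | Improved, effect 3.55 for all | Not improved, effect 3.55 for all | Ratio of the two improved shares |
|---|---|---|---|---|
| 4.47 | 1 − Φ(1.118) = 0.132 | 1 − Φ(0.324) = 0.373 | 0.627 | 0.35 |
| 7.59 | 1 − Φ(0.659) = 0.255 | 1 − Φ(0.191) = 0.424 | 0.576 | 0.60 |
| 13.42 | 1 − Φ(0.373) = 0.355 | 1 − Φ(0.108) = 0.457 | 0.543 | 0.78 |

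With no CPAP effect, 25-36% (office-type) or 13-25% (ambulatory-type) count as improved. Among 120 patients, that is about 31 to 43 or 16 to 31.

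With the same 3.55 mmHg effect in everyone, 54-58% or 58-63% count as not improved, about 65 to 69 or 69 to 75 patients. By construction, none of them had a smaller CPAP effect than the rest.

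If any fall counts as improvement, the share not improved is still 1 − Φ(3.55 / SD of change): 32-40% (office-type) or 21-32% (ambulatory-type).

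**The case against.** **Benefit may simply mean improvement, and this is an exploratory cohort.** This stands in part. The solution to Question 1 is purely predictive, and objective 1.1 is largely so. The cohort design itself is not at fault. But CPAP efficacy in 2.2, limits on treatment benefit in the Question 2 solution, and patients likely to benefit in IV.(1) go beyond prediction. If only prediction is meant, the correction costs nothing.

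**Random variation does not create a false predictor.** This is correct. Variation unrelated to the index weakens an association. In a simulation of 120 patients with no CPAP effect, retest correlation 0.7 and a baseline separate from the entry reading, the index was significant in 5-6% of trials, with an AUC of 0.50. A reader might infer from the shares above that the index would probably prove spurious. The documents do not support that: it would take non-CPAP change correlated with the index, and none is documented.

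**Regression to the mean from the entry reading.** A reader might expect a definite artefact here. Neither its size nor its direction can be fixed: the mean in the source population is not given, and inclusion routes (3) and (4) set no upper blood pressure limit.

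**Lifestyle change as a rival cause.** The background says that some patients reach normal pressure without drugs, and that the cohort includes patients who ask for non-pharmacological management. A reader might infer a lifestyle co-intervention. The text does not establish one, since CPAP is itself non-pharmacological.

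**The illustration rests on assumed values and would apply to any single-arm blood pressure cohort.** True. It shows scale only; the conclusion follows from the missing comparator.

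**Conclusion.** Wrong as written. Contents 1-2 can support statements about what predicts, or is associated with, blood pressure change during CPAP. They cannot support statements about who benefits from CPAP or what limits its efficacy.

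That conclusion rests on the protocol's text alone. The size rests on the assumed SDs, retest correlations and threshold, and on the protocol's 3.55 mmHg. Under these, the number expected to improve with no CPAP effect is 60-78% (office-type) or 35-60% (ambulatory-type) of the number expected when everyone has that effect.

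The finding does not say that the index fails to predict, that CPAP has no effect, or that the study must be randomised.

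**What to change.** Limit the Contents 1-2 conclusions to *predicts blood pressure change during CPAP* and *factors associated with blood pressure change during CPAP*. The places to change are:
- II.2, items 2.1 and 2.2;
- II.4, Question 1 and the solution to Question 2;
- IV.(1), Expected Results;
- II.1, where the objectives speak of benefit.

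The solution to Question 1 already has suitable wording and can serve as the model. State also that the self-selected non-CPAP groups of Component 3 will not be used to support a claim of CPAP benefit from Contents 1-2.

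The change is to wording only, with no new patients or measurements. The downside is a more modest claim for the index.

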### **III. Research Protocol and Technical Approach**

1. Study Design: Through a cohort study, this research aims to: ① explore innovative sleep-blood pressure indices; ② elucidate factors influencing suboptimal blood pressure improvement following CPAP therapy in OSA patients; ③ determine whether sleep aids alleviate insomnia and awakenings, thereby enhancing CPAP compliance and improving blood pressure.
2. Study Population: Participants will be recruited from the Sleep Medicine Center and Hypertension Department of Anzhen Hospital.

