### **(2) Evaluation Metrics**

1. Propose and validate an innovative sleep-blood pressure metric.
2. Publish two SCI papers (Q1 and Q2 journals).

This protocol strictly adheres to the Good Clinical Practice (GCP) guidelines and Anzhen Hospital's Special Management Measures for High-Level Research. It integrates all technical details of the application and has mitigated common risks of ethical rejection (funding disclosure, vulnerable subject protection, and intervention rationale).

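### The protocol promises to validate the sleep-blood pressure index, but plans only to derive its cut-off (and possibly the index) in one 120-patient cohort

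*Protocol*

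**What the plan says.** Validation is promised twice. Section II, objective 1.1 is to "Validate innovative sleep-blood pressure parameters for screening OSA patients who benefit from blood pressure improvement after CPAP therapy". Section IV, Evaluation Metrics, item 1 is to "Propose and validate an innovative sleep-blood pressure metric".

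The planned work is set out in Section II, Research Content 2.1: a cohort study of characteristics of patients whose blood pressure improved on CPAP, "obtaining a sleep-blood pressure index and its cutoff value for predicting CPAP treatment benefits". Section III, Study Design, describes the same aim as to "explore innovative sleep-blood pressure indices".

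The patients are allocated in Section III, item 5 (Sample Size Estimation). For the index and the factors that limit improvement it says "this project will enroll 120 OSA patients receiving CPAP therapy (Research Content 1-2"). The only other group it names belongs to the sleep-aid component and is described as "80 patients with insomnia combined with OSA or frequent awakenings during CPAP use (Research Content 3"). On their source, Section III, item 2 says: "Participants will be recruited from the Sleep Medicine Center and Hypertension Department of Anzhen Hospital".

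On the status of the index, Background section (2) says "we developed a sleep-blood pressure index that accurately reflects blood pressure fluctuations during respiratory events", whereas Research Content 2.1 treats the index as something the study will develop and obtain.

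**The concern.** Validating a screening rule means showing how it performs in patients who played no part in building it. A cut-off obtained from the blood pressure outcomes of the CPAP cohort is fitted to that cohort, so its sensitivity and specificity there are apparent values and too high on average. If the index is also chosen or shaped using those outcomes, its AUC is inflated as well.

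The product of this component is a rule for telling, before treatment, who is likely to gain a blood pressure benefit from CPAP. If derivation-sample accuracy is presented as validated, readers will on average expect better performance than new patients will show.

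**Working it through.** **1. Promise against allocation.**

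- Promised: validation (objective 1.1; evaluation metric 1).
- Planned: obtaining an index and cut-off in one cohort (Research Content 2.1), described elsewhere as exploring (Study Design).
- Patients: 120 for Research Content 1-2 and 80 for Research Content 3, so at most 120 + 80 = 200. No split sample, second site or later recruitment is named, and recruitment is from one hospital.
- The 80 cannot simply serve as a validation set. They are selected for insomnia or frequent awakenings, and Section III, item 4 groups patients by treatment choice, including a sleep aid with CPAP, trazodone alone and no treatment.

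The 120 cannot be reproduced: the item cites preliminary findings and gives no AUC, improver share, power or precision target. The figures below therefore illustrate the size of the problem under stated assumptions.

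**2. Optimism of a cut-off chosen and judged in the same 120 patients.** Assumptions, none in the protocol: one pre-fixed index, normal with equal variance in improvers and non-improvers; separation d = √2 · Φ⁻¹(AUC); 35% or 50% improvers; cut-off c maximising J = sensitivity + specificity − 1. True J at the chosen cut-off is Φ(c) − Φ(c − d). Means over 10,000 simulated cohorts per row:

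| True AUC | Improvers | Apparent J | True J | Excess | Excess ÷ true |
|---|---|---|---|---|---|
| 0.50 | 35% | 0.113 | 0.000 | 0.113 | – |
| 0.50 | 50% | 0.106 | 0.000 | 0.106 | – |
| 0.65 | 35% | 0.292 | 0.196 | 0.096 | 49% |
| 0.65 | 50% | 0.286 | 0.196 | 0.090 | 46% |
| 0.70 | 35% | 0.359 | 0.270 | 0.089 | 33% |
| 0.70 | 50% | 0.355 | 0.271 | 0.084 | 31% |
| 0.75 | 35% | 0.432 | 0.348 | 0.084 | 24% |
| 0.75 | 50% | 0.426 | 0.349 | 0.077 | 22% |
| 0.80 | 35% | 0.506 | 0.429 | 0.077 | 18% |
| 0.80 | 50% | 0.502 | 0.431 | 0.071 | 16% |

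At AUC 0.70, apparent sensitivity is 0.69 against 0.63–0.65 true, and specificity 0.67 against 0.63–0.64. These are averages: for an informative index the apparent J is at or below the true one in 9–15% of samples. The mean apparent AUC stays within 0.001 of the true AUC, so the AUC of a pre-fixed index is not inflated. A second simulation (30% or 50% improvers, AUC 0.50 to 0.80, 3,000 runs per setting) gave an excess of 0.07 to 0.12.

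**3. If the index is also picked on outcome.** Taking the best of 10 uninformative candidates at n = 120, in whichever direction fits, gives a mean AUC of about 0.60–0.61. The best of 20 gives about 0.62. The number of candidates is an assumption.

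**4. What internal correction recovers.** Bootstrap optimism correction (400 cohorts × 200 resamples), J as apparent / corrected / true:

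- AUC 0.50: 0.114 / 0.041 / 0.000 (35%); 0.110 / 0.040 / 0.000 (50%).
- AUC 0.65: 0.290 / 0.225 / 0.198 (35%); 0.282 / 0.220 / 0.196 (50%).
- AUC 0.75: 0.426 / 0.368 / 0.348 (35%); 0.427 / 0.373 / 0.347 (50%).

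Share of the excess removed, for example at AUC 0.65 with 35% improvers: (0.290 − 0.225) ÷ (0.290 − 0.198) = 0.065 ÷ 0.092 = 71%. Across the six settings it is 64–74%.

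**5. Why not hold patients out.** Setting aside 40 of the 120 leaves 12 improvers (30%) to 20 (50%). Around a sensitivity of 0.75 the 95% half-width is 1.96 · √(0.75 × 0.25 ÷ 12) = 0.245, or 0.190 with 20. With all 120 (36 to 60 improvers) it is 0.141 to 0.110. A small hold-out is a weak check.

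**The case against.** The strongest reply is that the promise covers parameters and a metric, not the cut-off. The index may be built purely by synchronising continuous blood pressure with polysomnography, without sight of outcomes. The 120 patients would then be a legitimate first test of it, and its AUC would be sound. This stands for the AUC of a fixed index. It does not rescue the cut-off: objective 1.1 is about screening patients, which needs a cut-off, and Research Content 2.1 obtains that cut-off from this cohort.

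The past tense in Background section (2) is weak evidence that a formula exists, because the protocol uses the past tense for planned work elsewhere (Section III, items 3 and 4). That is fair, and the status of the index is best treated as unclear rather than as a firm contradiction.

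A statistical analysis plan not shown may specify bootstrap or cross-validation. The absence of a resampling method from the protocol is therefore not a fault. But such a plan could not turn a single-cohort derivation into an independent validation.

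The size is also moderate and rests on assumptions. At AUC 0.70 the gap in sensitivity is about 0.04–0.06. The standard error of a sensitivity of 0.69 is √(0.69 × 0.31 ÷ 42) = 0.07 with 42 improvers and 0.06 with 60. This is true, but optimism is a bias in one direction, and an interval centred on the apparent value does not correct it. Finally, harm arises only if apparent accuracy is reported as validated, and the objective and the metric invite exactly that.

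**Conclusion.** The concern holds. The protocol claims validation in two places, while its content and patient allocation support only a derivation. This follows from the text alone and needs no assumption.

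The size does need assumptions: 120 patients, a Youden cut-off, one pre-fixed normal index, 35% or 50% improvers. With true AUC 0.65 to 0.80, apparent J is then too high by about 0.07 to 0.10 on average, close to half the true value at AUC 0.65 and about a sixth at 0.80. A useless index would show about 0.11 against 0. Selecting the index on outcome would add to this and would inflate the AUC too. The study can proceed, but the claim should be corrected.

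**What to change.** - Reword objective 1.1 and evaluation metric 1 to derive and internally validate, in line with the exploratory wording in Study Design. Reserve the word validated for an independent cohort.
- Add one sentence saying whether the index formula is already fixed or will be obtained from the cohort. Where possible, fix the formula and the cut-off rule before outcomes are seen.
- Keep all 120 patients for derivation. In the protocol or the statistical analysis plan, repeat every outcome-driven step (cut-off choice, and index selection if any) inside bootstrap resamples or repeated cross-validation. Report optimism-corrected sensitivity and specificity as the main result, with corrected AUC if the index is selected on outcome.

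The cost is wording in two places, one clarifying sentence and a few lines of analysis code. The headline accuracy will be somewhat less favourable, and internal correction leaves some optimism (roughly a quarter to a third of the excess in the settings above).
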